9.5.2 Statistical Methods for Efficacy Analyses

All efficacy endpoints will be analyzed based on the FAS population. Unless otherwise specified, all efficacy data will be included in efficacy analyses. A Hochberg testing procedure will be implemented in this study for multiplicity adjustment. LDA method will be used for the analysis of the continuous endpoints, and stratified M&N method will be used for the analysis of the binary endpoints.

Primary Efficacy Analysis

The primary endpoints, the percent change from baseline in F-VASI score at Week 24, will be analyzed using a LDA model for repeated measures. This model will use all available data on F-VASI at baseline and all post-baseline timepoints. In this model, time will be treated as a categorical variable so that no restriction is imposed on the trajectory of the means over time. The analysis model will adjust for treatment, visit, treatment by visit, and baseline vitiligo status (stable, active) and previous JAK inhibitor use (yes, no). Point estimates, 95% CI and p-value for the treatment differences will be provided. If there are a small number of responses in one or more strata, for the purpose of analysis, strata will be combined to ensure a sufficient number of participants and responses in each stratum. Details regarding the

combining of strata will be specified in the SAP prior to database lock based on a blinded review of response by stratum. An unstructured covariance matrix will be used to model the correlation among repeated measurements.

Sensitivity Analyses

In addition to the analysis approach specified above for the primary endpoint analysis section, the following sensitivity analyses will be used to assess the robustness of the primary analysis approach.

Multiple-imputation Analysis

For all participants with missing baseline F-VASI assessment, single imputation (only once) will be implemented based on baseline stratification factors. All post-baseline missing F-VASI assessments will be handled using multiple imputation (MI) under the missing-at-random (MAR) assumption.

Tipping-point Multiple-imputation Analysis

Tipping point as described in Ratitch et al. (2013) [Ratitch, B., et al 2013] will be conducted. In this approach, missing data are first imputed for all visits under the MAR assumption, and then the worsening/shift is applied. This is repeated with increasing the delta-shift (worsening) until the result is no longer statistically significant.

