9.8 Sample Size and Power Calculations

This study will randomize 55 participants into each treatment group and has >80% power to demonstrate the superiority of at least 1 dose of MK-6194 over placebo at an overall 2-sided 0.0499 alpha-level, if the underlying treatment difference in percent change from baseline at Week 24 in F-VASI score is -20%. The power and sample size are based on the following assumptions: 1) a 15% drop out rate, 2) a standard deviation of 33%, pooled across treatment groups.

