### 3.3.3 Derivations of Efficacy Endpoints

Baseline for efficacy variables is defined as the last non-missing value measured on or before the first study intervention.

CCI

CCI

Percent change from baseline is defined as the value at a specific visit minus the baseline value, divided by baseline value and multiplied by 100%, ie,

$$\%Change\ from\ Baseline\ in\ F-VASI = \frac{Post\ Baseline\ F-VASI - Baseline\ F-VASI}{Baseline\ F-VASI} \times 100\%$$

A negative percent change from baseline signifies an improvement.

The extent of depigmentation is expressed by the following 6 percentages: 10%, 25%, 50%, 75%, 90%, or 100%. Area with no depigmentation will be 0% and will not be considered for VASI calculation.

- 100% depigmentation: no pigment is present;
- 90% depigmentation: specks of pigment are present;
- 75% depigmentation: the depigmented area exceeds the pigmented area;
- 50% depigmentation: the depigmented and pigmented areas are equal;
- 25% depigmentation: the pigmented area exceeds the depigmented area;
- 10% depigmentation: only specks of depigmentation are present.

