### 3.5.2 Statistical Methods for Efficacy Analyses

All efficacy endpoints will be analyzed based on the FAS population. Unless otherwise specified, all efficacy data will be included in efficacy analyses. A Hochberg testing procedure will be implemented in this study for multiplicity adjustment. LDA method will be used for the analysis of the continuous endpoints, and stratified M&N method will be used for the analysis of the binary endpoints.

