#### **Primary Efficacy Analysis**

The primary endpoint, the percent change from baseline in F-VASI score at Week 24, will be analyzed using a LDA model for repeated measures. This model will use all available data on F-VASI at baseline and all post-baseline timepoints up to Week 24. In this model, time will be treated as a categorical variable so that no restriction is imposed on the trajectory of the means over time. The analysis model will adjust for treatment, visit, treatment by visit, and baseline vitiligo status (stable, active) and previous JAK inhibitor use (yes, no) based on IRT values. The treatment difference in terms of the mean percent change from baseline at Week 24 will be estimated and tested from this model. Point estimates, 95% CI and p-value for the treatment differences will be provided. An unstructured covariance matrix will be used to model the correlation among repeated measurements. If the unstructured covariance structure fails to converge with the default algorithm, an autoregressive AR(1) or compound symmetric (CS) structure will be used. The LDA method assumes that the mechanism for missing data is MAR. In this study, it is expected that MAR/MCAR mechanisms will underlie most of the missingness, and the proportion of data that are MNAR, driven solely by unobserved values of the study endpoints, will be small. Reasons for discontinuation from the study may include lack of efficacy, AEs, relocation, withdrawal of consent and protocol deviations. Missing data caused by a participant's relocation or data processing issues are likely to be MCAR. Missing data caused by discontinuations due to lack of efficacy may belong to MAR because this type of discontinuation may depend on the observed efficacy outcomes. The MAR or MNAR mechanisms might each underlie the other reasons to some extent. If the assigned study intervention in large part determines the loss of data for these other reasons (such as AEs), the mechanism may be close to MAR since the intervention assignment is an observed variable and included in the analysis model.

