### 3.8 Sample Size and Power Calculations

This study will randomize 55 participants in each treatment group and has >80% power to demonstrate the superiority of at least 1 dose of MK-6194 over placebo at an overall 2-sided 0.05 PPD alpha-level, if the underlying treatment difference in percent change from baseline at Week 24 in F-VASI score is -20%. The power and sample size are based on the following assumptions: 1) a 15% drop out rate, 2) a standard deviation of 33%, pooled across treatment groups.

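### If the unstructured fit fails and percent-change variance rises over visits, the SAP's fallback to AR(1) or CS with one common variance understates the Week 24 standard error

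*SAP*

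**What the plan says.** Protocol 9.5.2 names one covariance structure for the primary model: "An unstructured covariance matrix will be used to model the correlation among repeated measurements". It gives no fallback. SAP 3.5.2, Primary Efficacy Analysis, repeats the unstructured choice and adds the rule at issue: "If the unstructured covariance structure fails to converge with the default algorithm, an autoregressive AR(1) or compound symmetric (CS) structure will be used".

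The SAP describes the model's data and target in the same paragraph: "This model will use all available data on F-VASI at baseline and all post-baseline timepoints up to Week 24", and "The treatment difference in terms of the mean percent change from baseline at Week 24 will be estimated and tested from this model". The response scale is set in SAP 3.3.3: "Percent change from baseline is defined as the value at a specific visit minus the baseline value, divided by baseline value".

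The paragraph names no heterogeneous-variance structure, no other algorithm or starting values for the unstructured fit, no empirical (sandwich) standard error, and no order between AR(1) and CS. SAP 3.5.2 analyses T-VASI in the same way and applies the same model to each imputed data set, so both inherit the rule.

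**The concern.** AR(1) and CS, as named, assume the same residual variance at every visit. The primary test uses only the Week 24 contrast. If percent change is less variable at early visits than at Week 24, the common variance averages small early variances with a large late one. The model then reports a Week 24 standard error that is too small, so the p-value is too low and the confidence interval too narrow.

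Rising variance is plausible here. Percent change is zero for everyone at baseline by construction, and participants have more time to diverge by Week 24 than by Week 2. The SAP controls multiplicity through Hochberg ("A Hochberg testing procedure will be implemented in this study for multiplicity adjustment"), but that procedure takes the two p-values as given and cannot repair a wrong standard error behind them.

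**Working it through.** **Inputs.** 55 per arm, 15% dropout, SD 33% and difference -20% (Protocol 9.8, SAP 3.8). F-VASI at Weeks 2, 4, 8, 12, 18 and 24 after baseline (Protocol 1.3.1). Two dose-placebo comparisons under Hochberg (SAP 3.7). The protocol computes power "at an overall 2-sided 0.0499 alpha-level" and the SAP "at an overall 2-sided 0.05"; the difference has no bearing here. No SD by visit is given, so every visit pattern below is an assumption.

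**The plan's own figure.** Evaluable per arm: 55 × 0.85 = 46.75. SE = 33 × √(2/46.75) = 6.83, and 20/6.83 = 2.93. Power for one comparison = Φ(2.93 − 1.96) = 83.4%. For at least one dose under Hochberg, with both doses at -20 and a shared placebo arm (correlation 0.5), it is 89.2%. The stated power above 80% is reproduced and is not in question.

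**Chance of reaching the fallback.** An unstructured matrix over six visits has 6 × 7/2 = 21 parameters, against about 165 participants. Non-convergence is not the expected case.

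**Closed form for CS, complete data.** With a separate mean for each arm and visit, the Week 24 estimate is the raw mean difference, with true SE 33 × √(2/55) = 6.29. The CS model uses the average of the six visit variances:

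- pooled SD = √(mean of the six squared SDs)
- ratio r = pooled SD / 33
- actual two-sided error = 2 × [1 − Φ(1.96 r)]

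Example: SDs 20, 22, 25, 28, 31, 33 have squares summing to 4343. The mean is 723.8, the pooled SD 26.9 and r = 0.815. The reported SE is 26.9 × √(2/55) = 5.13 and the error 11.0%.

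| Assumed SD at Weeks 2, 4, 8, 12, 18, 24 | Pooled SD | r | Reported SE (true 6.29) | Error per comparison |
|---|---|---|---|---|
| 33 throughout | 33.0 | 1.00 | 6.29 | 5.0% |
| 24, 25.8, 27.6, 29.4, 31.2, 33 | 28.7 | 0.869 | 5.47 | 8.9% |
| 20, 22, 25, 28, 31, 33 | 26.9 | 0.815 | 5.13 | 11.0% |
| 10, 14, 20, 25, 29, 33 | 23.3 | 0.705 | 4.44 | 16.7% |
| proportional to √weeks, 33 at Week 24 | 22.7 | 0.687 | 4.32 | 17.8% |

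**Simulation for AR(1) and CS with dropout.** REML fits, no treatment effect, 3 × 55 participants, six visits, 15% missing-at-random dropout, 2,000 trials per scenario. The true correlation was AR(1) at 0.85 or exchangeable at 0.6. Ranges cover both fitted structures.

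| SD pattern | Reported SE | True SE | Error per comparison | Familywise (Hochberg) |
|---|---|---|---|---|
| 20 to 33 | 5.2–5.5 | 6.6–6.8 | 11–13% | 13–15% |
| 10 to 33 | 4.5–4.7 | 6.7–6.8 | 18–19% | 21–23% |

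A smaller simulation (800 trials, 15% dropout) of a mild rise from 24 to 33 gave 10% (CS) and 9% (AR(1)) per comparison, and 12% and 11% familywise. Its intermediate SDs need not match the linear ones in the first table.

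**Where the condition fails.** With or without dropout, constant SD gave 5.1–6.4% per comparison. SD falling from 33 to 25 gave 2.0–2.6%.

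**With the remedy.** In the two rising patterns of the second table, a sandwich standard error on the same AR(1) and CS fits gave 5.4–5.9% per comparison and 5.0–5.3% familywise. A converged unstructured fit gave 4.8–5.2% and 4.5–4.9%.

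**Limits.** The 2,000-trial runs left out the two stratification covariates and did not model baseline as a response. Their Monte Carlo error is about 0.5 to 0.9 points.

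**The case against.** The strongest reply is that two things must happen together: the unstructured fit must fail, and variance must rise. The first is unlikely with this many participants and visits. The second is not documented. That reply stands, and it limits the weight of the point. It does not make the rule sound, because a fallback matters only on the occasion when it is used.

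Four stronger readings are tempting, and the documents do not support them.

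- **That Week 2 variance is near zero.** No visit-level SD is given, and rating noise alone could make early variance material. Entry F-VASI may be 0.3 (Protocol 5.1). One fully depigmented fingertip unit scores 0.03, so misjudging one moves percent change by 0.03/0.3 = 10 points. A grade step from 75% to 50% changes a lesion's score by 25/75, a third. Starting the SD at 8 (8, 12, 18, 24, 29, 33) gives 18% in closed form, and 20–23% per comparison with 26–27% familywise in the smaller simulation. That is the most extreme pattern tried and should not be the headline.
- **That the test is anti-conservative whenever the fallback is used.** It is not, under constant or falling variance.
- **That baseline zeros make the unstructured matrix singular, so the fallback becomes the primary analysis.** The SAP says baseline data are used but not how they enter. Its imputation model uses percent change at post-baseline visits. The wording is ambiguous and the claim is unproven.
- **That AR(1) is materially wrong because visits are unequally spaced.** The gaps after Week 2 are 2, 4, 4, 6 and 6 weeks, but no effect of spacing has been isolated.

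The open choice between AR(1) and CS is a real gap, but a small one: their error rates differed by at most about 3 points. SAP 3.5.2 also says that details will be finalised before the final database lock.

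**Conclusion.** The point holds in conditional form. The SAP states a rule that can give a wrong primary p-value; this is more than missing detail. If the unstructured fit fails and variance rises from Week 2 to Week 24, the Week 24 standard error is understated. Error is then about 9% to 19% per comparison instead of 5%, and about 11% to 23% familywise after Hochberg.

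The direction follows from algebra. The size depends on assumed SD patterns ending at 33, which the documents neither confirm nor rule out. The trigger is unlikely, so this is a change that should be made, not a fault in the planned main analysis. The sample size and the unstructured model are unaffected.

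**What to change.** Before database lock, replace the fallback sentence in SAP 3.5.2 with a fixed sequence:

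1. Retry the unstructured fit with other starting values or another algorithm.
2. If it still fails, use the first structure that converges in this order: heterogeneous Toeplitz, heterogeneous AR(1), heterogeneous CS.
3. Use the empirical (sandwich) standard error for any structure other than unstructured.
4. Remove homogeneous AR(1) and CS.

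State that the same rule applies to T-VASI and to each imputed data set.

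The cost is a few sentences, with no new data. The sandwich standard error is slightly less stable in small samples, which is acceptable at 55 per arm. It corrects only the variance: a misspecified covariance can still bias the estimate under missing-at-random dropout. That is why retrying the unstructured fit comes first and flexible structures come before simple ones. Other orderings would also serve; what matters is that variances may differ by visit and that the order is fixed in advance.

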## **Sensitivity Analyses**

In addition to the analysis approach specified above for the primary endpoint analysis section, the following sensitivity analyses will be used to assess the robustness of the primary analysis approach.

### **Multiple-imputation Analysis**

For all participants who are missing baseline F-VASI assessment, single imputation (only once) will be implemented based on baseline vitiligo status (stable, active) and previous JAK inhibitor use (yes, no). All post-baseline missing F-VASI assessments will be handled using MI under the missing-at-random assumption.

A fully conditional specification method that assumes the existence of a joint distribution for all variables will be used. A regression model including treatment group, stratification factor(s) and percent change from baseline in F-VASI scores at all post-baseline visits up to Week 24 will be specified for the fully conditional specification method. The randomization seed will be set to 6194007. The MI procedure will be repeated 50 times and the imputed endpoint will be analyzed using the same analysis model as the primary analysis based on each of the datasets. SAS PROC MIANALYZE will be used to generate the final treatment differences between MK-6194 treatment group and placebo group and the statistical inferences, including hypothesis testing, and 95% CI will be combined using Rubin's rule.

### **Tipping-point Multiple-imputation Analysis**

Tipping point analyses as described in Ratitch et al. (2013) [Ratitch, B., et al 2013] will be conducted. In this approach, missing data are first imputed for all visits under the MAR assumption, and then the worsening/shift is applied. This is repeated with increasing the delta-shift (worsening) until the result is no longer statistically significant. Specifically, after generating 50 datasets using MI procedure and before analyzing each of the imputed datasets, add a constant c from each of the imputed values of the active arm (to the detriment of active) and a constant d from each of the imputed values of the placebo arm. SAS PROC MIANALYZE will be used to combine results using Rubin's rule.

## **Secondary Efficacy Analysis**

The secondary efficacy endpoint, the percent change from baseline in T-VASI at Week 24, will be analyzed similarly as the primary endpoint.

[Table 2](#) summarizes the analysis strategy of the primary and secondary efficacy endpoints.

Table 2 Analysis Strategy for Key Efficacy Variables

Endpoint/Variable (Description, Time Point)	Primary vs Supportive Approach	Statistical Method	Analysis Population	Missing Data Approach
Primary Endpoint/Hypothesis 1				
Percent change from baseline in F-VASI at Week 24	P	LDA	FAS	Model based
	S	LDA	FAS	Multiple Imputation
	S	LDA	FAS	Tipping Point Multiple Imputation
Secondary Endpoint 2				
Percent change from baseline in T-VASI at Week 24	P	LDA	FAS	Model based
FAS=Full Analysis Set; F-VASI= Facial Vitiligo Area Scoring Index; LDA=longitudinal data analysis; T-VASI= Total Vitiligo Area Scoring Index P=Primary approach; S=Supportive approach.				

The efficacy analysis mentioned above will be performed at the end of the Double-Blind Treatment Period (Week 24). Additional descriptive analyses will be performed at the end of the Blinded Extension Period (Week 52). No comparison between treatment groups will be involved in any of the analyses for blinded extension. Details of the analysis plan will be finalized in the SAP before the final database lock.

### **Exploratory Efficacy Analysis**

Descriptive statistics will be provided for time points with measurements from at least three different participants for the following continuous F-VASI and T-VASI endpoints. The analysis will utilize all observed data, with no imputation for missing values. The derivation details of the following endpoints are in Section 3.3.3:

- Percent change from baseline in F-VASI at all timepoints
- Percent change from baseline in T-VASI at all timepoints

The proportion of participants achieving 25%, 50%, 75%, and 90% improvement in F-VASI and T-VASI will be provided across time points for the following binary endpoint. The derivation details of the binary endpoints are in Section 3.3.3.

The proportion of participants achieving 50%, 75%, and 90% improvement in F-VASI and T-VASI at Week 24 will be analyzed using the stratified M&N method with the following stratification factors: vitiligo status (stable, active) and previous JAK inhibitor use (yes, no) based on IRT values. The estimated treatment difference along with the corresponding 95% CIs will be presented. The post-baseline missing F-VASI assessments will be handled using MI under the missing-at-random assumption. The derivation details of the binary endpoints are in Section 3.3.3.

Descriptive statistics for change from baseline of the VitiQoL score will be provided for time points with measurements from at least three different participants. The analysis will utilize all observed data, with no imputation for missing values. The derivation details of the binary endpoints are in Section 3.3.3.

The proportion of participants in each level for the following categorical endpoints will be provided across time points. The analysis will utilize all observed data, with no imputation for missing values. The derivation details of the binary endpoints are in Section 3.3.3.

#### VNS

- PGI-S on facial area and PGI-S on total body area
- PGIC/M on facial area and PGIC/M on total body area
- CGI-S on facial area and CGI-S on total body area
- CGI-C on facial area and CGI-C on total body area
- CCI

In addition, the proportion of participants achieving treatment success as defined below for the following categorical endpoints will be provided across time points.

- VNS of 4 (A lot less noticeable) or 5 (No longer noticeable)
- PGI-S on facial area of None or Mild
- PGI-S on total body area of None or Mild
- PGIC/M on facial area of Better or Much Better
- PGIC/M on total body area of Better or Much Better
- CGI-S on facial area of None or Mild
- CGI-S on total body area of None or Mild
- CGI-C on facial area of Better or Much Better
- CGI-C on total body area of Better or Much Better

### 3.5.3 Statistical Methods for Safety Analyses

Safety and tolerability will be assessed by clinical review of AEs and other relevant parameters, including laboratory tests, and vital signs.

#### 3.5.3.1 Overall Safety Assessment

The overall safety evaluation will include a summary (ie, frequency and percentage) by treatment group of participants with at least one AE, drug-related AE, serious AE, serious drug-related AE, discontinuation from study intervention due to an AE, and AE resulting in death.

Point estimates and 95% CIs for the differences between treatment groups in the percentages of participants with events will be provided for AEs that occur in at least 4 participants in any treatment group using the M&N method [Miettinen, O. and Nurminen, M. 1985]. This threshold for the number of participants with AEs was chosen because the 95% CI for the between-group difference in percent incidence will always include zero when fewer

participants per group have events and thus would add little to the interpretation of potentially meaningful differences. CIs that are not adjusted for multiplicity should only be regarded as helpful descriptive measures for the review of the safety profile and not as a formal method for assessing statistical significance of between-group differences. Figures and/or plots will be provided as needed.

For continuous safety measures, such as laboratory, and vital signs, summary statistics for baseline, on-treatment, and change from baseline values will be provided by treatment group.

Table 3 summarizes analysis strategy for safety endpoints in this study.

Table 3 Analysis Strategy for Safety Parameters

Safety Endpoint	Descriptive Statistics	95% Between-group CI	Graphical Display
Any AE	X	X	
Any serious AE	X	X	
Any drug-related AE	X	X	
Any serious drug-related AE	X	X	
Discontinued study treatment due to AE	X	X	
AE that resulted in death	X		
Specific AEs or SOCs (incidence $\geq 4$ participants in any treatment group)	X	X a	X a
Change from Baseline Results (Labs, Vital Signs)	X		
AE=adverse event; CI=Confidence Interval; SOC=System Organ Class. a : Threshold for incidence will be applied for CI and Graphical Display.			

The safety analysis mentioned above will be performed at the end of the Double-Blind Treatment Period (Week 24). Additional descriptive analyses will be performed at the end of the Blinded Extension Period (Week 52). No comparison between treatment groups will be involved in any of the analyses for Blinded Extension Period. Details of the analysis plan will be finalized in the SAP before the final database lock.

